3. Exploratory Aim: Describe the pharmacological and non-pharmacological strategies Veterans are using to manage pain and their perceived helpfulness. This will provide insights into the effects of the current opioid restrictions on pain management strategies. These strategies & their perceived helpfulness will be assessed using the Pain Management Strategies Survey at baseline, 6 weeks, 3, and 6 months.

Study Design

The proposed study is a multi-site, double-blind, two-arm, parallel, randomized controlled trial. At-risk Veterans will be randomly assigned to one of two groups: 1) Acceptance and Commitment Therapy (ACT); or 2) Attention Control (AC). Primary and secondary outcomes will be measured at 6 weeks, 3 and 6 months but 6 months will be the primary outcome endpoint for determining mediator effects. Data collected at postoperative week 1 will be used as potential moderators of treatment response.

Schema

Inclusion and Exclusion Criteria

The target study population is veterans undergoing unilateral total knee arthroplasty (TKA) who are at-risk for persistent postsurgical pain (i.e. report moderate to severe preoperative pain in the presence of anxiety and/or depression OR report severe pain and absent anxious and depressive symptoms). A total of 430 participants (215 per group) will be recruited to achieve 150 subjects per group.

Inclusion Criteria

Participants must meet all the following inclusion criteria to participate in this study:

- Veteran;
- 18 years old or older;
- Having unilateral total knee arthroplasty (TKA);
- At risk for pain, anxiety, depression and/or stress, or pain catastrophizing defined as 1, 2, 3 or 4 (below):
 1. Worst pain greater than or equal to 7 on BPI (severe pain)
 2. Worst pain 3-6 (moderate to severe pain) on BPI AND anxiety symptoms (anxiety score greater than or equal to 6 on the DASS 21 or DASS stress score greater than or equal to 10)
 3. Worst pain 3-6 (moderate to severe pain) on BPI AND depressive symptoms (depression score greater than or equal to 7 on the DASS 21)
 4. Worst pain 3-6 (moderate to severe pain) on BPI AND PCS score greater than or equal to 20

Exclusion Criteria

All candidates meeting any of the exclusion criteria will be excluded from study participation.

Exclusion criteria are:

- Inability to complete study forms because of language/literacy barrier;
- Bipolar or psychotic disorder;
- History of brain injury (moderate to severe TBI, other severe injury);

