For variables in the primary aim (pain severity and functioning), efficacy of ACT compared to AC at 6 weeks, 3 months and 6 months will be tested using linear mixed model analysis for repeated measures. The fixed effect in the model will include intervention group, time, and intervention*time interaction effect. The model will also include site, workshop (cluster) within intervention, and subject as random effects. Test of mean contrast will be used to compare between treatment group means and mean change from baseline to 6 weeks, 3 and 6-months post-TKA between ACT and AC. P-values will be adjusted using Bonferroni's method to account for the number of tests performed. The efficacy of ACT versus AC will be expressed as the group mean difference with a 95% confidence interval (CI), using the SAS STAT (14.1) MIXED procedure.

For the secondary aim (A), efficacy of ACT compared to AC on anxiety symptoms, depressive symptoms, pain acceptance, and engagement in values-based behavior will be compared using linear mixed model for repeated measures. Intervention group mean differences will be estimated and tested as described in the analysis for the Aim1 variables.

For the primary and secondary aim analyses, it is expected that randomization will lessen the need for covariate or moderator adjusted analyses. However, if any demographic, baseline, time from workshop to surgery, or perioperative variables (i.e. perioperative anesthesia/analgesic, postoperative complications, postop day 1 pain and function, etc.) are found to differ between intervention groups, the model will be expanded to include these variables as covariates or effect moderators to estimate and test intervention group mean differences, or odds ratio, controlling for these variables.

In addition to the analyses described above for the primary & secondary outcome measures, similar linear mixed model analyses that include all randomized subjects will be performed. This secondary analysis will include surgery status in the model to contrast the impact of the intervention on those with and without surgery.

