The AC workshop will cover the following topics: a) the pathophysiology of postoperative pain and how it differs from preoperative pain, b) the role of contextual factors (e.g., depressive or anxiety symptoms, expectation) on the experience of pain, d) the role of inflammation in pain and healing, e) types of pain medications and other pain relief strategies provided following surgery, and f) goals of pain medications. Participants in the AC workshop will receive one manual.

Booster

A research team member will consult with each participant at their workshop to schedule the "booster" session and all postop assessments. They will also, again, be given instructions for accessing the post-op surveys online through REDCap. Two weeks after surgery, one of the workshop facilitators will call participants to check on them and conduct an individualized phone "booster" session. This phone call will

last 20-40 minutes. A second booster, lasting 20-40 minutes, will be conducted if any of the following occurs: 1) the participant reports within the 6-week assessment window that there are surgical complications, new health problems, and/or emotional issues that are affecting recovery and/or causing significant distress, 2) a study psychologist determines within the 6-week assessment window that there are surgical complications, new health problems, and/or emotional issues that are affecting recovery and/or causing significant distress, 3) the participant has surgery four or more months after attending a workshop. Participants will receive a reminder call/message approximately 1 day before the session. Participants who have consented to participate in the Department of Veterans Affairs' Annie mobile Short Message Service (SMS) text messaging, will receive a short text message reminding them of their scheduled "booster" session a day before the session.

Randomization

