This study will use a cluster randomization approach where the unit of randomization will be the workshops. Randomization will occur right before each workshop so that all participants attending that workshop will be randomized to that intervention (i.e. ACT vs. AC). Statistician [name] will generate the randomization sequence to ensure adequate distribution of the two interventions over the study period. Randomization will be stratified by site (i.e. Iowa City versus Houston). The randomization sequence will be maintained by the Statistician in a password protected file. This file will be used to generate concealed envelopes maintained and accessed by a facilitator at each site. Allocation of workshop to intervention group will remain concealed for facilitators until approximately one week before the workshop to allow for the needed preparation. Workshop allocation to intervention group will remain concealed for all other study personnel and participants until the beginning of the workshop when all invited participants have arrived. Those in attendance will receive the assigned intervention. This allocation approach will eliminate pre-treatment withdrawals, minimize the potential for experimenter and participant bias by protecting the randomization sequence in a central location, maintain concealment of treatment allocation until the last possible moment, and keep the participants and outcome assessors blinded to treatment.

Virtual Workshops

The randomization scheme for BCM should be used for all virtual workshops.

Blinding

This is a double-blind study. Participants are blinded to which treatment is the treatment of interest and outcome assessors will be blinded to which treatment participants receive. The treatment allocators (i.e. project coordinators) and the workshop facilitators will not be blinded so they can be available throughout the study to answer questions regarding treatment. It is essential for them to know which group the participant is in, in case they need to troubleshoot the treatment.

Participants will complete the Workshop Usefulness Survey (Workshop Question 6wk) in REDCap at the end of their 6-week assessments and the Participant Blinding Question in REDCap at the end of their 6-month assessment. Assessors will complete the Assessor Blinding Question (Workshop Question 6mo) in REDCap at the end of each participants' 6-month assessment.

Post-Op Evaluations

6 Weeks, 3 Months and 6 Months Post-Op Surveys

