At 6 weeks, 3 months and 6 months postop, all Veterans will receive REDCap automated survey invitations and, if they have consented to participate in the Department of Veterans Affairs' Annie mobile Short Message Service (SMS) text messaging, short text messages reminding them to take the survey. If participants prefer, paper copies of these surveys will be mailed to them with a cover letter. At 6 weeks, the survey will include: BPI; DASS-21; PCS; OQ-45.2; KOOS - postop; CPAQ; CPVI; Promise Sleep; Complications; and workshop usefulness (6wk). At 3 months, the survey will include: BPI; DASS-21; PCS; PMSS (postop); OQ-45.2; KOOS - postop; CPAQ; CPVI; and Promise Sleep. At 6 months, the survey will include: BPI; DASS-21; PCS; PMSS (postop); OQ-45.2; KOO - postop; CPAQ; CPVI; Promise Sleep; Workshop Usefulness (6mo); and COVID-19 Impact.

Survey Review

In each case, after the participant has completed the surveys, the RAs will cross-check the medications reported in the BPI and DASS-21 with those in the medical record and discuss discrepancies with the participant.

Data Collection and Quality Assurance

Data management

The Study Coordinator at the Coordinating Site will be responsible for:

1. Designing and maintaining the REDCap data collection site as well as the Tracking Database
2. Ensure all data is stored so that blinded study personnel do not have access to any data that would un-blind them.
3. Conduct regularly scheduled audits (including hard-copy-to-electronic-copy checks) and data quality checks

REDCap

All data collection forms will be available through a REDCap (Research Electronic Data Capture) database (supported by the institutional CTSA) and patients can directly enter data into these forms. They will enter data into a central database through their computer or a tablet provided in the clinic. This will eliminate error in data entry, and reduce time necessary for data entry, cleaning and analysis. Range checks will be programmed into the data entry system when the nature of the data allows so that it will not permit invalid values to be entered into the database.

When a data collection session is completed, the RA will review electronic forms for completeness and validity. The RA will resolve all queries and will enter an override for all values that have been confirmed as being accurate. Reports will also be run periodically to confirm or correct questionable values. All changes will be tracked through the REDCap audit trail.

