10. Recordings of workshops and fidelity ratings: (S:) IOW Services Drive\Research [name] Closed\PrePARE

Strategies for minimizing missing data

Strategies will include:

1. Reviewing all surveys for completeness before finalizing
2. Conducting weekly texts and/or phone calls, as needed, to remind participants to complete daily logs
3. Contacting participants postoperatively to review data entry requirements, provide them with verbal and written directions for filling out and submitting daily logs, reviewing contact information, and identifying appropriate methods/times for follow-up contacts.

Protocol Deviations

Protocol deviations will be entered in the study's Tracking Database are known to happen in order to compile an electronic log for reporting purposes.

Monitoring

Data will be routinely monitored at the time of data collection. REDCap will be used to collect data and the researchers will be prompted at the end of each session to check missing entries. Regular team meetings will be held where researchers can report ongoing data collection concerns to ensure proper adherence to the protocols and high-quality data collection.

Data Collection Instruments

Demographics/Medical Information

Description: Demographic information will be collected via a questionnaire including age, sex, race, ethnicity, marital status, education, and household income. Medical information on smoking, BMI, co-morbidities and all medications will also be collected from the medical record. For both demographic and medical information, the medical record will be reviewed, and discrepancies will be discussed with the Veteran and resolved to facilitate complete and accurate data. These variables will be used to characterize the sample and examine possible influences on treatment response.

Brief Pain Inventory Short Form (BPI-SF)

Outcome Measure: Pain (intensity)

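### Postoperative week 1 data are named as moderators, but they have no defined source and arise after the workshop; pre-randomisation moderators should be prespecified instead

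*Combined protocol and SAP*

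**What the plan says.** The Précis, under Study Design, fixes the outcome times ("Primary and secondary outcomes will be measured at 6 weeks, 3 and 6 months") and then adds: "Data collected at postoperative week 1 will be used as potential moderators of treatment response". It names no variable or instrument for week 1.

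The Post-Op Evaluations section has one subsection, "6 Weeks, 3 Months and 6 Months Post-Op Surveys". It begins "At 6 weeks, 3 months and 6 months postop, all Veterans will receive REDCap automated survey invitations" and lists the instruments for each of the three occasions. Under Booster, the first postoperative contact is described: "Two weeks after surgery, one of the workshop facilitators will call participants to check on them".

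Two other places refer to early postoperative data:

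- **Strategies for minimizing missing data.** One strategy is "Conducting weekly texts and/or phone calls, as needed, to remind participants to complete daily logs". Another is to contact participants after surgery and "provide them with verbal and written directions for filling out and submitting daily logs".
- **Data Analysis.** Among the variables that may enter the models as covariates or effect moderators are "perioperative anesthesia/analgesic, postoperative complications, postop day 1 pain and function, etc". They enter only if they are found to differ between the intervention groups. The same condition applies to demographic and baseline variables and to the time from workshop to surgery.

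**The concern.** A moderator analysis asks which patients gain more from ACT than from attention control. It needs a variable that is defined, collected and unaffected by the treatment. As written, the week 1 sentence meets none of these conditions with certainty. Staff following the schedule would find no week 1 form to administer. An analyst following the sentence would have either no data or data recorded after the intervention had been delivered.

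At stake is the interpretability of any moderator result. With no list of variables and no interaction model, moderators could be chosen after the outcomes are known. If a post-workshop measure were used, a subgroup defined by low week 1 pain in the ACT arm might consist partly of Veterans whose pain ACT had already lowered. Comparing it with the same subgroup in the control arm would no longer be a randomised comparison.

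**Working it through.** **Step 1. Is there a week 1 source?**

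| Place in the document | What it provides | Week 1 data? |
|---|---|---|
| Post-Op Evaluations | Surveys at 6 weeks, 3 months, 6 months, with instruments | None listed |
| Booster | Facilitator call two weeks after surgery, part of the intervention | No |
| Locations of data by type | Screening, pre-randomisation, allocation, booster, postop assessments, deviations | No week 1 or daily-log entry |
| Data Collection Instruments | Descriptions of individual instruments | No week 1 form or daily log described |
| Strategies for minimizing missing data | Reminders and directions for daily logs | Content, start and duration undefined |
| Data Analysis | Day 1 pain and function | No collection source stated |

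Three scheduled postoperative assessments are listed, none at week 1. Three references to early data (week 1, day 1, daily logs) have no defined procedure.

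**Step 2. Would week 1 data be valid moderators?** The Randomization section allocates each workshop just before it takes place, and Study Interventions places the workshop before surgery. The order is therefore baseline, randomisation, workshop, surgery, day 1, week 1. The Data Analysis section gives the working model: ACT acts by improving how Veterans cope with pain after the operation. On that model, early postoperative pain or function may lie on the path from treatment to outcome, so it cannot cleanly identify who benefits.

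**Step 3. Does the Data Analysis section supply a valid alternative?** It allows baseline variables as effect moderators, but only when the groups differ on them. Imbalance is a reason to consider adjustment. It says nothing about effect modification: a perfectly balanced variable can modify the effect, and an imbalanced one need not. No intervention-by-moderator interaction is specified.

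**Step 4. Are valid candidates already collected?** Yes. Before randomisation, consented Veterans complete the BPI, PCS and DASS-21, and eligible ones go on to others, including STAI-Trait, PCL-5 and CPAQ.

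**Step 5. What would baseline interaction tests cost in power?** Inputs from Sample Size: difference 8, SD 18, ICC 0.06, 6 per workshop, significance level 0.0167 (two-sided assumed), power 0.80.

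- Design effect: 1 + (6 − 1) × 0.06 = 1.30. With a cluster-level noncentral t, 25 workshops of 6 per arm give power 0.811 and 24 give 0.791, so the stated 150 per group reproduces.
- For a binary moderator splitting each arm in half, the interaction is a difference of two effects, each estimated on half the sample. Its standard error is about twice that of the main effect. At the same level and power, the detectable interaction is about 2 × 8 = 16 KOOS-ADL points.
- If the moderator varies evenly within workshops, the workshop effect cancels, giving about 16 × √(0.94/1.30) = 13.6 points.
- Five moderators (BPI worst pain, three DASS-21 subscales, PCS) on three primary measures (BPI Pain Severity, KOOS ADL, KOOS QoL) make 5 × 3 = 15 tests.

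Only large interactions would be detected reliably, so the exploratory label is needed.

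**The case against.** The strongest reply is that this is a wording gap with little consequence, and much of that stands. No primary, secondary or exploratory aim poses a moderator question, and the sentence says only that the moderators are potential. Baseline variables also have some role: a conditional one in Data Analysis, and a general one under Demographics/Medical Information, where demographic and medical variables are to be examined for influence on treatment response.

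Silence in the lists is imperfect evidence too. The content of the Schema is not available in the text, so a week 1 entry there cannot be excluded. The instrument section is not exhaustive: OQ-45.2 and STAI-Trait, for example, are administered but not described. The 6-week survey list omits the PMSS that the Exploratory Aim places at 6 weeks. The daily logs and the day 1 reference suggest that some early data may be collected.

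Three stronger readings are therefore tempting but unsupported:

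- **That the trial cannot say who responds to ACT.** Moderation by baseline variables remains possible with the data collected.
- **That no analysed Veteran will have a week 1 record.** The text shows that the data are undefined, not that they are absent.
- **That reminders go to logs rather than to the endpoint surveys.** Post-Op Evaluations provides automated invitations, text reminders for those who agreed to them, and paper copies on request. The postoperative assessments are scheduled at the workshop, and the missing-data strategies include a completeness review of all surveys.

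None of this answers the timing problem, which would remain if a week 1 form were found.

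**Conclusion.** The point holds in a limited form. The named week 1 moderators have no defined instrument, variable or collection point in the written schedule. They would also be measured after randomisation and the workshop, so they are not valid moderators even if collected. The rule in Data Analysis does not repair this, because it selects moderators by group imbalance and itself includes post-workshop variables.

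The effect is confined to the moderator statement. The primary and secondary comparisons, the mediation analysis and the sample size do not use week 1 data. The source finding assumes that the Schema shows no week 1 assessment. The timing finding does not depend on that assumption; it rests on the stated order of workshop and surgery. This is worth correcting before analysis, but it does not threaten the trial's main conclusions.

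**What to change.** 1. **Précis, Study Design.** Replace the week 1 sentence with, for example: *Potential moderators are the pre-randomisation values of BPI worst pain, the DASS-21 depression, anxiety and stress scores, and PCS. Each will be tested as an intervention-by-moderator interaction on the 6-month primary outcomes. These analyses are exploratory.* In the repeated-measures model this is the intervention-by-time-by-moderator term, with the contrast taken at 6 months.
2. **Data Analysis.** Remove post-workshop variables (time from workshop to surgery, perioperative variables, complications, day 1 pain and function) as effect moderators, and drop group imbalance as the criterion for selecting moderators.
3. **Reconcile** Study Design, Data Analysis, Post-Op Evaluations and the missing-data strategies. If week 1, day 1 or daily-log data are in use, list their variables, source and timing and treat them as early postoperative outcomes. If not, delete the references. Confirm which applies before editing, so that a procedure in use is not removed by mistake.

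The cost is a wording amendment and a short addition to the analysis plan. No new data collection is needed. The downside is a set of low-powered interaction tests (15 with the list above), to be reported as estimates with confidence intervals and given no confirmatory status.

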Consented participants will be asked to complete the Agreement to Participate; Demographics, SCQ, BPI, PCS and DASS 21. This should take 20-30 minutes. Participants who meet inclusion criteria (Worst pain greater than or equal to 7 on BPI [severe pain]; OR worst pain 3-6 [moderate to severe pain] [on BPI AND anxiety symptoms [anxiety score greater than or equal to 6 on the DASS 21 or DASS stress score greater than or equal to 10]; OR worst pain 3-6 [moderate to severe pain] on BPI AND depressive symptoms [depression score greater than or equal to 7 on the DASS 21]; OR worst pain 3-6 [moderate to severe pain] on BPI AND PCS score greater than or equal to 20) will then be instructed to complete a set of surveys (i.e., OQ-45.2; CAGE; DAST-10; PCL-5; KOOS - baseline; STAI-Trait; PMSS (baseline); CPAQ; CPVI; PROMIS sleep: COVID impact). Completing these surveys should take approximately one hour. These surveys may be completed online on paper. The medical record will be reviewed for this same information (i.e. demographics, medical information, medications). Any discrepancies in medical information will be discussed with the participant to facilitate complete and accurate data. Once completed, participants will be scheduled for a workshop and asked to order their lunch (if attending an in-person workshop). Participants will also be given instructions for accessing the post-op surveys online through REDCap and given contact information for study personnel.

Participants who have completed the pre-randomization assessment will be considered “enrolled”.

Study Interventions

Veterans will attend either a 1-day ACT workshop or a 1-day AC workshop prior to surgery. These workshops may be held online via Zoom to minimize risk of exposure to COVID-19. Two psychotherapists, trained in ACT, will provide the workshops in groups of 3-10 Veterans. Each workshop will last 5-6 hours.

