Description: The DASS is a self-report scale to measure the negative emotional states of depression, anxiety and stress. It contains 21 items, 7 items per subscale (depression, anxiety and stress) (Lovibond & Lovibond, 1995). Participants are asked to rate the extent to which they have experienced each state over the past week with a 4-point scale (from 0 = did not apply to me at all to 3 = applied to me very much). Scores are summed per subscale and then multiplied by 2 for possible scores on each subscale ranging from 0 to 42 (Lovibond & Lovibond, 1995). Higher scores indicate more severe symptoms of depression, anxiety and stress. Internal consistency of the DASS-21 subscales in a non-psychiatric sample were high (0.88 for Depression, 0.83 for Anxiety, and 0.85 for Stress) (Osman et al., 2012). Depression, Anxiety and Stress subscales also showed adequate convergent validity ($r = 0.55$, 0.44 , and 0.61 , respectively) with Affective Distress subscale of the Multidimensional Pain Inventory and adequate discriminant validity ($r = -0.67$, -0.50 , and -0.63 , respectively) with Mental Health subscale of the SF-36 in elderly patients with persistent pain (Wood et al., 2010).

Telephone Administration of the Memory Impairment Screen (MIS-T)

Outcome Measure: Memory Impairment

Description: The MIS-T is a telephone version of the well-validated in-person Memory Impairment Screen (MIS) as a screening test for dementia. The telephone interviewer presents 2 (of 4) target words and asks participants to repeat the words to ensure that they were heard correctly. The interviewer then demonstrates a category cue associated with one of the target words. The participants are asked to choose the word that matches the category cue. The interview then demonstrates the category cue for the other word and this procedure is repeated for the other two target words. After a several minute interference period with no semantic tasks,

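### The depression eligibility cut-off of 7 cannot occur under the protocol's own DASS-21 scoring, and no section states which scale the three DASS cut-offs use

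*Combined protocol and SAP*

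**What the plan says.** All references are to the combined protocol and SAP.

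- **Inclusion Criteria (Précis).** There are four routes to eligibility. Two use the DASS-21 and both require worst pain of 3-6: one asks for "anxiety score greater than or equal to 6 on the DASS 21 or DASS stress score greater than or equal to 10", the other for a "depression score greater than or equal to 7 on the DASS 21". The other two do not use the DASS-21: "Worst pain greater than or equal to 7 on BPI (severe pain") and "Worst pain 3-6 (moderate to severe pain) on BPI AND PCS score greater than or equal to 20".
- **Summary of post-consent screening and pre-randomization assessment.** The same routes and the same three DASS cut-offs are repeated, again with no scale named.
- **Data Collection Instruments, Depression Anxiety and Stress Scale (DASS-21).** This is the only place that says how the instrument is scored. "It contains 21 items, 7 items per subscale (depression, anxiety and stress"), and each item is rated "with a 4-point scale (from 0 = did not apply to me at all to 3 = applied to me very much"). Then: "Scores are summed per subscale and then multiplied by 2 for possible scores on each subscale ranging from 0 to 42".

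**The concern.** Doubling a whole number always gives an even number. A cut-off of 7 is therefore not a score that anyone can obtain under the stated rule, although it is an ordinary value on the undoubled 0-21 sum. That raises the question of which scale the cut-offs were meant for, and neither section that lists them answers it.

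The cut-offs help decide who with worst pain of 3-6 counts as at risk and enters the trial. If they are applied on a scale other than the intended one, the trial either admits people below the intended symptom level or turns away people who should have been eligible. The DASS-21 also supplies secondary outcomes and candidate mediators, so the entry bar bears on how much baseline distress there is to improve. Without a stated scale, a reader of the results cannot tell how symptomatic the enrolled moderate-pain group had to be.

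**Working it through.** **Inputs.** Seven items per subscale, each scored 0, 1, 2 or 3, with the sum multiplied by 2 (DASS-21 instrument section). Cut-offs: anxiety 6, depression 7, stress 10 (Inclusion Criteria, repeated in the screening summary).

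**Step 1: reproduce the stated range.** The largest undoubled sum is 7 × 3 = 21, and doubled it is 21 × 2 = 42. The smallest is 0. The stated range of 0 to 42 is reproduced. The attainable scores are 0, 2, 4, ..., 42.

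**Step 2: are the cut-offs attainable?** Anxiety 6 and stress 10 are even and can occur. Depression 7 is odd and cannot. On the doubled scale, a rule of at least 7 acts as at least 8.

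**Step 3: the bar under each reading.** Let S be the undoubled item sum and c the cut-off.

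- Cut-off on the doubled score: 2S ≥ c, so the smallest qualifying S is c/2 rounded up.
- Cut-off on the undoubled sum: S ≥ c, so the smallest qualifying S is c.

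| Subscale | c | Smallest S, doubled reading | Smallest S, undoubled reading | Ratio | S values whose status changes | Same, as doubled scores |
|---|---|---|---|---|---|---|
| Anxiety | 6 | 6/2 = 3 | 6 | 6/3 = 2.0 | 3-5 | 6-10 |
| Depression | 7 | 7/2 = 3.5, so 4 | 7 | 7/4 = 1.75 | 4-6 | 8-12 |
| Stress | 10 | 10/2 = 5 | 10 | 10/5 = 2.0 | 5-9 | 10-18 |

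**Step 4: whose eligibility changes?** Worst pain of 7 or more qualifies whatever the DASS score, and PCS of 20 or more qualifies anyone with worst pain 3-6. Among the rest (worst pain 3-6, PCS below 20):

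- undoubled anxiety ≥ 6, depression ≥ 7 or stress ≥ 10: eligible on both readings;
- undoubled anxiety ≤ 2, depression ≤ 3 and stress ≤ 4: ineligible on both;
- at least one of anxiety ≥ 3, depression ≥ 4, stress ≥ 5, but anxiety ≤ 5, depression ≤ 6 and stress ≤ 9: eligible on the doubled reading only.

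Only the last group is affected. Everyone eligible on the undoubled reading is also eligible on the doubled one, so the discrepancy runs in one direction.

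**Example.** Worst pain 5, PCS below 20, three anxiety items rated 1 and the other four rated 0, undoubled depression at most 3 and stress at most 4. The anxiety sum is 3, doubled 6. This person is eligible if the cut-off of 6 is a doubled score and ineligible if it is an undoubled sum.

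**Step 5: how many?** The documents give no distribution of DASS, PCS or worst-pain scores, so the number in the affected group cannot be calculated.

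**The case against.** The strongest reply is that the sections do not contradict one another. The two lists of cut-offs are identical, there is one scoring rule, and no section mentions an undoubled score. Staff who follow everything written arrive at one workable rule: doubled anxiety of at least 6, stress of at least 10, depression of at least 7 (in effect 8). Every candidate can be classified, and two of the three cut-offs sit properly on the scale. This stands. A reader might infer that the bar varies by a factor of two according to which section is followed. The documents do not support that: the higher bar arises only if the cut-offs were set on, or are applied to, undoubled sums.

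Three other tempting inferences also go too far.

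- **That the cut-offs came from the undoubled scale.** Within the documents, the odd value of 7 is the only pointer, and it does not settle the matter.
- **That the two sites score differently.** Nothing suggests it. Forms feed a central REDCap database, and screening data are to be held in common databases. On the other hand, no section describes a programmed eligibility calculation, and the REDCap range checks would not show whether a valid sum had been doubled before comparison with the cut-off.
- **That treatment effects are diluted.** This is possible for the distress measures but is neither shown nor quantified. The primary outcomes are BPI pain severity and the KOOS ADL and QoL subscales, and the design deliberately admits people with severe pain and no distress.

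The reply does not remove the point that a literal reading means accepting an eligibility value that cannot be scored, with no statement of scale to show that this was intended.

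**Conclusion.** The point holds in a limited form. The depression cut-off is not an attainable score under the protocol's only DASS-21 scoring rule, and the scale for all three cut-offs is unstated. If they are doubled scores, the bar is an undoubled sum of 3, 4 and 5 for anxiety, depression and stress. If they are undoubled sums, it is 6, 7 and 10, higher by a factor of 1.75 for depression and 2.0 for the other two. That gap is conditional on the second reading, which is plausible but is an assumption.

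It would be wrong to infer that every candidate with worst pain 3-6 and PCS below 20 is affected. Only those who meet at least one DASS criterion on the doubled reading and none on the undoubled reading change status, and their number is unknown.

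The consequence is for the composition of the trial population and for generalizability. The DASS-21 is completed before workshops are randomized, so the ambiguity does not bias the comparison between arms. It should be corrected because it concerns an entry criterion and the correction is simple.

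**What to change.** 1. Reconcile Inclusion Criteria, the post-consent screening summary and the DASS-21 instrument section. Beside the cut-offs, state whether they refer to the doubled (0-42) or undoubled (0-21) score, and use values attainable on that scale. For conversion only, undoubled 6, 7 and 10 correspond to doubled 12, 14 and 20. Which thresholds are right is for the study team to confirm; this review does not propose any.
2. Apply that single rule in the eligibility calculation at both sites.
3. Check which scale screening has actually used. If it matches the confirmed rule, nothing more is needed.
4. Only if it differs, recheck the screened candidates in the affected group. If undoubled sums were used but the doubled rule is confirmed, the errors are refusals, to be counted and reported. If doubled scores were used but the undoubled rule is confirmed, some randomized participants may not meet it; report a sensitivity analysis that excludes them.

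The cost is a one-line protocol clarification, made in each place the cut-offs appear, and a check of the eligibility calculation. A short audit of screened candidates is added only if step 3 shows a mismatch.
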